5.2.4 Physical examination

At day 1 of each treatment cycle, a physical examination will be performed to assess disease progression. In case Progressive Disease (PD) is suspected based on physical examination, imaging should be performed.

ECOG Performance Status:

The ECOG performance status is a scale used to assess how a patient's disease is progressing and how the disease affects daily living abilities. Performance status is graded using the following scale from 0 to 5:

- 0- Fully active, able to carry on all pre-disease performance without restriction
- 1- Restricted in physically strenuous activity but ambulatory and able to carry out work of a light or sedentary nature, *e.g.* light house work, office work
- 2- Ambulatory and capable of all self-care but unable to carry out any work activities, Up to about more than 50% of waking hours
- 3- Capable of only limited self-care, confined to bed or chair more than 50% of waking hours
- 4- Completely disabled. Cannot carry on any self-care. Totally confined to bed or chair
- 5- Dead

5.2.5 Constitutional symptoms

All patients will be evaluated for constitutional symptoms at the same time points when a physical examination is indicated in the [Flow Chart](#). Analysis of constitutional symptoms will be based on the following parameters which have to be reported in the eCRF:

- Unintentional weight loss (10% or more within the previous 6 months)
- Significant fatigue (ECOG PS 2 or worse; inability to work or perform usual activities)
- Fevers higher than 38.0°C (for 2 or more weeks without other evidence for infection)
- Night sweats (for more than 1 month without evidence of infection)

5.2.6 Minimal Residual Disease (MRD)

MRD detection will follow a flow cytometry protocol in a central laboratory according to established standards as *e.g.* published by the European Research Initiative on CLL (ERIC) [[R14-4986](#)]. Modifications according to updated guidance are possible.

For MRD assessment, approximately 10 mL of peripheral blood will be required from each patient at each of the time points specified in the [Flow Chart](#), *i.e.* at screening, before Day 1 of Cycle 1 (C1D1), and at the end of Cycle 3, 6, 9 and 12. For those patients continuing beyond Cycle 12, assessments have to be performed at the end of Cycle 16, 20, 24, at the EOT visit, and at the first follow-up visit.

MRD negativity is defined as less than 1 leukemic cell per 10000 leukocytes detected in a multi-parameter flow cytometry with adequate sensitivity. In case peripheral blood is MRD negative, approximately 4 mL of bone marrow aspirate will be taken from the patient in addition to peripheral blood at the next time point when a blood MRD assessment is scheduled in order to confirm MRD negativity in bone marrow.

At any time when a BM is performed to confirm a clinical CR or CRi, a blood and bone marrow sample should be sent for MRD.

At all timepoints when MRD sample is obtained, a CBC with differential will be performed at the central laboratory. This CBC/differential from the central laboratory should be used for disease/response assessment whenever possible.

Detailed instructions for sampling, handling, storage, and shipment of the MRD samples will be provided in the laboratory manual included in the ISF. Date of sampling will be recorded in the eCRF.

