²EOT visit – When the decision is taken to permanently discontinue the study medication for PD. The EOT visit should be performed as soon as possible, but before a new CLL treatment is started. Assessments do not need to be repeated if the EOT is done within 14 days after a response assessment visit. For patients who complete Cycle 24 and terminate BI 836826 in the absence of PD, the assessments specified for EoT and EoR can be also combined at the time of EoR.

³End of Residual Effect Period (EoR) Visit is to be completed 30 days after the EOT (+ 7 days). Information collected at this visit should include all new AEs and ConMeds that occurred since the EOT and follow-up of AEs ongoing at the time of the EOT. In case the patient completes Cycle 24 and terminates treatment with BI 836826 according to protocol in the absence of PD, the assessments indicated for the EOT and EoR visit in the [flowchart](#) may be performed once, at the time specified for the EoR visit

⁵There will be an additional contact with regard to the End of Trial status as soon as the end of the whole trial is reached (see [Section 8.6](#)). Contact can be either a clinic visit or phone call. Visits will include vital status and anti-cancer treatment for CLL at the time of contact.

⁶Ibrutinib will be administered according to the package insert for CLL indication. Patients must continue to secure sourcing of ibrutinib For patients with CR, CRi or PR (MRD negative) at each of the disease assessments, may continue with monthly infusions of BI 836826, until progression, undue toxicity or to the maximum of 24 cycles. Daily dosing of ibrutinib can continue as per the label and at the discretion of the investigator or physician.

⁷PE to be performed on Day 1 of every Cycle, before start of BI 836826 infusion and at EOT

⁸Single, resting 12 lead ECG to be performed on Day 1 of every Cycle and EOT, or whenever deemed necessary by the investigator (See [Section 5.3.4](#)).

⁹HBV DNA monitoring is only applicable to patients who are HBc antibody positive at screening (see [Section 5.3.3.4.1](#)). Patients who are HBc antibody positive at screening will be monitored for potential HBV reactivation by quantitative HBV DNA at visit 1 of every even course (Cycle 14, 16, 18, etc...) and at the EOT

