¹⁰Safety lab tests (blood and urine) do not have to be repeated if previous tests are within 48 hours of visit. Additional safety labs may be performed as deemed necessary by the investigator. If neutropenia CTCAE Grade 3 or 4 is observed for more than 7 days, repeat until return to a Grade 2 or lower in order to capture the duration of severe neutropenia (see [Section 5.3.3](#)). Coagulation tests have only to be performed at every other cycle and at EOT visit.

¹¹Quantitative CMV DNA PCR or pp65 antigen to be performed every other cycle, starting with Cycle 13 (see [Section 5.3.3.4.2](#)).

¹²Urine Pregnancy test is mandatory for all female patients of childbearing potential. Test must be performed within 7 days prior to first treatment on C1 Day 1, at CxV1 of every other cycle starting with Cycle 13 (i.e. Cycle 15, 17, etc..) and at EOT. To ensure early detection of pregnancy, test might be repeated as necessary during the treatment period. (See [Section 5.3.3.1](#))

¹³ Follow-up visits and accompanying assessments will no longer be required after approval of CTP Amendment 1

¹⁴ Follow-up visits will no longer be required after approval of CTP Amendment 1

¹⁷ Disease assessment has to be performed prior to starting treatment at Day 1, >=21 days after BI 836826 administration and prior to start of next cycle (preferably between D21 and D28); Every 4 Cycles.

¹⁸ MRD in peripheral blood is to be performed at the end of Cycles 16, 20, 24 and at EOT. A bone marrow aspirate and biopsy, including MRD evaluation according to IWCLL guidelines is mandatory in patients who meet the criteria for CR based on physical examination, complete blood count (two consecutive CBCs matching the criteria for CR), and imaging (see [Section 5.2.6](#)).

¹⁹ Every 16 weeks if clinically indicated; If a patient is in CR after a disease assessment, he/she may continue with the study treatment for up to the maximum of 24 cycles. A CT should be performed whenever a CR is suspected for the first time, if none was performed in the previous last 4 weeks and at EOT if none was performed in the previous last 4 weeks

²⁰ Sample collection will no longer be required after approval of CTP Amendment 1

²¹ Findings on physical examination with potential impact on response assessment should be confirmed by imaging.

²² Follow-up visits and accompanying assessments will no longer be required after approval of CTP Amendment 1

TABLE OF CONTENTS

TITLE PAGE	1
CLINICAL TRIAL PROTOCOL SYNOPSIS	2

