Each patient enrolled, completing the screening period and meeting eligibility will enter the run-in phase and start with ibrutinib monotherapy pre-treatment on Day -14 through Day -1. While AEs from this period will be collected, they will not constitute part of the DLT evaluation period for combination therapy. The dose for ibrutinib will be 420mg daily, orally.

Cycle 1:

Patients completing the screening period and run-in phase will start the combination treatment. For prevention of IRRs and tumor lysis syndrome the first administration of BI 836826 will be a pre-dose of 10 mg/ml on Day 1. Subsequent two doses will be 50% of the target dose on Day 2 and on Day 8, followed by 100% of the target dose on Day 15 of the first cycle. Patients will continue to receive ibrutinib on days 1-28 of cycle 1. DLTs from the start of the first BI 836826 infusion through the MTD evaluation period (Cycle 1) as well as other AEs will be used to assess dose escalation steps and to determine the MTD.

Cycle 2-4:

Patients will receive 100% of assigned dose of BI 836826 on days 1 and 15 of each cycle. Patients will continue to receive ibrutinib on days 1-28 of each cycle (2-4). At the end of Cycle 3 (Imaging and Laboratory) and Cycle 4 (Laboratory) disease assessment will be performed. Patients without disease progression of CLL will be allowed to continue with BI 836826 and ibrutinib.

Cycle 5-12:

Patients will receive 100% of assigned dose of BI 836826 on Day 1 of each cycle. Patients will continue to receive ibrutinib on days 1-28 of each cycle. Disease assessment will be performed every three cycles or 12 weeks, and will be performed at the end of every third cycle, i.e. Day 21 through Day 28 of Cycle 6, 9, and 12. Treatment with BI 836826 will be terminated at the end of cycle 12 in all patients who achieve PR (MRD positive), PR-L, Stable Disease (SD) or PD in the response assessment at the end of cycle 12. Patients who achieve a CR (MRD positive or negative) or a PR (MRD negative), may continue treatment with BI 836826 as outlined below for additional 12 cycles. Treatment with ibrutinib monotherapy may be continued according to label at the discretion of the investigator or the patient's physician.

Cycle 13-24 (patients with CR and MRD-negative PR only):

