6. INVESTIGATIONAL PLAN

6.1 VISIT SCHEDULE

The screening period is a maximum of 21 days prior to the start of the Run-In Phase. Patients who meet all trial eligibility criteria will continue into the Run-in phase and begin two weeks (+/- 2 days) of ibrutinib monotherapy dosing prior to the first infusion of BI 836826.

Treatment with BI 836826 will be administered in cycles of 28 days duration. The dose of BI 836826 will be tapered up to the target dose during Cycle 1 to mitigate the risk for IRRs and TLS. Treatment with BI 836826 starts with the first administration of 10 mg ('pre-dose') on Cycle 1 Day 1 (see [Section 3.1](#)), followed by 50% of the target dose of BI 836826 on Cycle 1 Day 2 and Cycle 1 Day 8. The first full dose of BI 836826 (100% of the target dose) will be administered on Cycle 1 Day 15.

In Cycles 2 to 4, patients will receive 100% of the target dose of BI 836826 on Day 1 and Day 15 of each cycle. In Cycles 5 to 12, BI 836826 will be administered at 100% of the target dose on Day 1 only. A response evaluation, including imaging (if clinically indicated), will be performed at the end of Cycle 3, 6, 9 (Day 21-28) and 12 (Day 21-30). Only those patients with CR, CRi, or MRD negative PR in the response assessment at the end of Cycle 12 will be allowed to continue with additional 12 Cycles of combination treatment or until relapse, undue toxicity, withdrawal of consent or until the end of the maximum treatment duration of BI 836826 at the end of 24 Cycles, whichever comes first. In patients who continue treatment beyond 12 cycles and proceed to Cycles 13-24, a response evaluation including imaging (if clinically indicated) will be performed at the end of Cycles 16, 20, and 24.

Once a patient stops the BI 836826 treatment, he/she will undergo an End of Treatment (EOT) visit.

In case the patient completes Cycle 12 or Cycle 24 and terminates treatment with BI 836826 according to protocol in the absence of PD, the assessments indicated for the EOT and End of REP (EoR) visit in the [flowchart](#) may be performed once at the time specified for the EoR visit.

In case a patient experiences PD, an EOT visit including imaging should be performed as soon as possible after discontinuation of BI 836826 and prior to initiation of subsequent therapy. An EoR visit should be performed 30 days (+ 7 days) after EOT.

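### The protocol tests eligibility to continue BI 836826 after Cycle 12 once in some sections and at every assessment in another, a difference of up to 8 infusions for a patient whose status changes

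*Protocol*

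**What the plan says.** Four places in the protocol make continuation a single decision at Cycle 12: the synopsis (duration of treatment), Section 3.1 (Treatment), Section 6.1 and Section 6.2.2. After that decision, Section 6.1 lets treatment run "until relapse, undue toxicity, withdrawal of consent or until the end of the maximum treatment duration of BI 836826", with Cycle 24 as the maximum. Section 6.2.2 gives the same stopping events.

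Footnote 6 of the Cycle 13-24 flow chart reads differently: "For patients with CR, CRi or PR (MRD negative) at each of the disease assessments, may continue with monthly infusions of BI 836826". It then adds progression, toxicity and the 24-cycle maximum as limits.

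The qualifying categories also vary. Section 4.1.4 says: "Patients who achieve a CR (MRD positive or negative) or a PR (MRD negative), may continue treatment with BI 836826". It does not mention CRi. Footnote 19 of the Cycle 13-24 flow chart says only: "If a patient is in CR after a disease assessment, he/she may continue with the study treatment".

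On MRD, Section 5.2.6 states: "MRD negativity is defined as less than 1 leukemic cell per 10000 leukocytes detected in a multi-parameter flow cytometry with adequate sensitivity". It does not say whether this refers to blood or marrow. Blood is sampled "at the end of Cycle 3, 6, 9 and 12", and then: "For those patients continuing beyond Cycle 12, assessments have to be performed at the end of Cycle 16, 20, 24". After a negative blood result, marrow is taken "at the next time point when a blood MRD assessment is scheduled in order to confirm MRD negativity in bone marrow".

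**The concern.** In Section 4.1.4 the MRD label alone decides whether a partial responder stops BI 836826 at Cycle 12 or may go on to Cycle 24. A rule with that effect should read the same wherever a site looks it up. Here a site working from Section 6.1 and a site working from the flow-chart footnote could treat the same later MRD result differently.

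The issue is still live. Section 2.1 stops recruitment but lets patients already on treatment complete the trial under the protocol. At stake are the amount of extended exposure and the length of safety observation that goes with it.

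**Working it through.** No power or sample-size figure bears on this point. The check compares the passages and counts infusions.

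**The continuation passages side by side**

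| Place in protocol | When status is tested | Who may continue |
|---|---|---|
| Synopsis, duration of treatment | After 12 cycles | CR, CRi, MRD-negative PR |
| Section 3.1, Treatment | End of Cycle 12 | CR, CRi, MRD-negative PR |
| Table 4.1.1:1 | Not stated | CR, CRi, MRD-negative PR |
| Section 4.1.4 | End of Cycle 12 | CR, MRD-negative PR; CRi not named |
| Section 6.1 | End of Cycle 12 | CR, CRi, MRD-negative PR |
| Section 6.2.2 | Cycle 12 | CR, MRD-negative PR; CRi not named |
| Flow chart to Cycle 12, footnote 24 | After an unspecified assessment | CR, CRi, MRD-negative PR |
| Flow chart Cycles 13-24, footnote 6 | Each assessment | CR, CRi, MRD-negative PR |
| Flow chart Cycles 13-24, footnote 19 | After an unspecified assessment | CR |

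**Infusion count**

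1. The plan's own figure: Cycle 1 has 4 infusions (Days 1, 2, 8, 15), Cycles 2-4 have 3 × 2 = 6, and Cycles 5-12 have 8. The total is 4 + 6 + 8 = 18, which matches the synopsis.
2. Cycles 13-24 have one infusion each, so 12 more. The maximum is 18 + 12 = 30.
3. Take a patient with MRD-negative PR at Cycle 12 who is MRD positive, still in PR, at Cycle 16. The progression criteria in Appendix 10.2 do not include MRD conversion, so this patient has not progressed.
4. Under Sections 6.1 and 6.2.2 the patient may continue to Cycle 24, for a total of up to 30. If footnote 6 is applied at Cycle 16, the patient no longer qualifies, and the total is 18 + 4 = 22. The difference is 30 − 22 = 8 infusions (Cycles 17-24), or 8 × 28 = 224 days between nominal last doses.
5. If the change is first seen at Cycle 20, the difference is 24 − 20 = 4 infusions.

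**Marrow timing under Section 5.2.6**

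The first negative blood result maps to the marrow as follows: Cycle 3 to 6, 6 to 9, 9 to 12, 12 to 16. In three of the four cases the marrow is available at or before the Cycle 12 assessment. Only a first negative at Cycle 12, in a patient who continues, puts it at Cycle 16. That is 4 infusions (Cycles 13-16) and nominally 4 × 28 = 112 days later. No passage says how negative blood with positive marrow is classed for continuation.

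**What the analysis sees**

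- The primary and secondary endpoints (RP2D, Cycle 1 DLTs, MTD) rest on data that precede this decision by many cycles, apart from the wider safety and efficacy evidence that may inform the RP2D.
- The on-treatment adverse event period ends 30 days after the last BI 836826 dose (protocol Section 7.3.4; SAP Sections 6.1 and 7.8.1.2), so its end moves with the last infusion.
- SAP Section 7.4 also presents DLT counts and model posteriors for the complete on-treatment period. Their follow-up length moves in the same way.
- SAP Table 6.2:1 has no violation category written for continuing past Cycle 12 without qualifying.

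**The case against.** The case for leaving this alone has four parts.

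- **Footnote 6 is loosely written.** It is grammatically incomplete, sits under the ibrutinib row, ends with much the same stopping events as Section 6.1, and says that patients may continue. It never says that a patient who turns MRD positive must stop. A reader might infer a mandatory stop, and the documents do not go that far. What stands is that the footnote makes qualifying status at each assessment the condition for continuing, and the other sections do not.
- **The CRi gaps look like shorthand.** Section 4.1.4 does not list CRi among those who stop at Cycle 12, Appendix 10.2 treats CRi as a CR with therapy-related cytopenia or hypocellular marrow, and most passages name it. Footnote 19 belongs to the imaging row and does not say that only CR qualifies. This stands, so these are secondary wording gaps.
- **Marrow timing.** A reader might infer that marrow confirmation comes too late for the Cycle 12 decision. The documents do not support that as a general statement. No continuation passage makes the marrow result decisive, and a first negative at Cycle 3, 6 or 9 gives a marrow by Cycle 12. A patient who stops has an end-of-treatment marrow that includes MRD. What remains is that the compartment and the handling of discordant results are undefined.
- **Impact is limited.** The endpoints concern dose and Cycle 1 toxicity, and the SAP plans an abbreviated report. This stands for the MTD. It does not remove the effect on individual exposure or on the whole-period safety displays.

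**Conclusion.** The inconsistency is real and worth correcting. The same MRD result at Cycle 16 leaves a non-progressing partial responder eligible for up to 8 further infusions under Sections 6.1 and 6.2.2, and not qualified under footnote 6. The omission of CRi and the undefined MRD compartment are lesser gaps in the same rule.

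The size rests on three assumptions: nominal 28-day cycles with no missed or delayed infusions; relapse in Sections 6.1 and 6.2.2 read as progression under Appendix 10.2; and footnote 6 applied as a condition at each assessment. The 8 infusions are a maximum for one such patient. A reader might want to turn this into a share of the approximately 20 planned patients. The documents do not support any such figure, because they give neither the number still on treatment nor the frequency of late MRD conversion.

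Cycle 1 DLT counts and the MTD determination are not affected.

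**What to change.** Reconcile the passages into one continuation rule, state it once, and have Sections 4.1.4, 6.1 and 6.2.2 and the flow-chart footnotes (24 in the first chart; 6 and 19 in the second) refer to it. The rule should make clear:

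- whether status is tested once at Cycle 12 or again at each later assessment;
- which response categories qualify, with CRi named or excluded explicitly;
- which compartment, blood or marrow, defines MRD negative for this decision, and how discordant results are classed.

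Which rule stands is for the sponsor to decide. No change to the timing of the aspirate is proposed here. The cost is protocol wording and a letter to sites, with no added procedure and no change to the dose-finding model or sample size.

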5.3 ASSESSMENT OF SAFETY

Safety will be assessed by:

- Overall incidence and severity of AEs, as well as seriousness and relatedness
- AE leading to treatment discontinuation
- AE leading to death
- AE of special interest
- Changes in safety laboratory parameters
- Changes in vital signs, physical examination, ECG

Changes in laboratory parameters and AEs will be graded according to US NCI CTCAE version 4.0 [[R10-4848](#)]. In addition, hematological toxicity based on laboratory values will be assessed using the criteria as described in IWCLL guidelines ([R10-4429](#)).

5.3.1 Physical examination

A physical examination including height (only at screening), weight and ECOG performance score (see [Section 5.2.4](#)) as well as the tumor size determination (see [Section 10.2](#)) will be performed at screening and at the time points specified in the Flow Chart. During the physical examination, the patient should be assessed for possible AEs.

5.3.2 Vital signs

Vital signs (blood pressure, pulse rate and body temperature) will be recorded at every visit during screening, treatment and follow-up, before proceeding with any other protocol specific procedure and after at least 5 minutes of rest. More frequent measurements of vital signs must happen on the days of study drug administration, at the investigator's discretion, or to detect possible IRRs which have then to be reported as AE. In case of IRR, the investigator should decide whether to intensify or prolong the monitoring of vital signs of the patient and to adapt patient's surveillance during subsequent applications.

5.3.3 Safety laboratory parameters

5.3.3.1 General safety laboratory parameters

Blood and urine samples have to be collected at the time points specified in the [Flow Chart](#). However, more frequent samplings may be done to perform additional safety laboratory

examinations whenever the investigator deems it necessary. Local laboratories of the sites will be used for safety laboratory assessments. Sample and handling will be performed in accordance with local site procedures.

- Hematology:** Hemoglobin, red blood count (RBC), white blood count (WBC) with differential: neutrophils, basophils, lymphocytes, monocytes, eosinophils - expressed preferably in absolute values percentages accepted (including Gumprecht shadow (Smudge Cells) and Large Unstained Cells (LUC)) and platelets
- Biochemistry:** Sodium, potassium, calcium, inorganic phosphate, creatinine, AST, ALT, Alkaline Phosphatase (AP), Lactate Dehydrogenase (LDH), Blood Urea Nitrogen (BUN), uric acid, total bilirubin. If total bilirubin is elevated, direct bilirubin should be provided.
If direct bilirubin is elevated, the following tests to assess haemolysis should be obtained in addition: direct antiglobulin test, reticulocytes, haptoglobin.
- Coagulation:** Activated Partial Thromboplastin Time (aPTT) in seconds, Prothrombin Time (PT) in seconds or International Normalized Ratio (INR) have to be measured at screening, at visit 1 of every other cycle and at the EOT visit
- Urine:** Urine pH, glucose, erythrocytes, leukocytes, protein, nitrite will be analysed by dipstick. In case of suspicion of a clinically relevant proteinuria, *i.e.* at least 2 positive results after prior negative tests, protein should be quantified in 24 hour urine
- Pregnancy test:** A pregnancy test in serum or urine needs to be obtained at the time points indicated in the Flow Chart in women of childbearing potential

